8.3.17.4. Proportion of patients with the ability to remain independent of ventilator support

The numbers and percentages of patients with the ability to remain independent of ventilator support at 18 months of age will be presented by overall and by subgroups, including subgroups, age at the time of treatment (≤ 4 months, >4 months).

The observed proportion achieving independent of ventilator support at 18 months of age will be compared to zero using a 1-sided Exact Binomial Test, along with the corresponding 97.5% confidence intervals. To make computation of the p-value possible, the value of 0.1% will be used in place of a literal zero.

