5.4. Clinical Studies

First-in-human trial AVXS-101-CL-101 is a completed 2-year trial which evaluated the efficacy and safety of AVXS-101 in 15 SMA Type 1 patients with 2 copies of *SMN2*. All patients have received a single IV dose of AVXS-101 in 2 cohorts: Cohort 1 (n = 3) received 6.7×10^{13} vg/kg and Cohort 2 (n = 12) received 2.0×10^{14} vg/kg (proposed therapeutic dose). After the End of Trial visit, patients were invited to participate in a long term follow up study conducted under a separate protocol.

- Based on data obtained in Study AVXS 101-CL-101, the following conclusions can be made regarding the efficacy of AVXS 101:
- AVXS 101 administration had a positive effect on survival. Twenty-four months after dosing, all 15 patients were alive and free of permanent ventilation 24 months after dosing and all Cohort 2 patients had survived free of permanent ventilation, a statistically significant difference compared with the natural history rate of 8% reported by Finkel et al 2014 [23].
- Based on independent video reviews, developmental milestones were achieved and maintained over time.
 - In Cohort 2, 11 patients (91.7%) could hold their head erect without support for ≥ 3 seconds and sit with support, 9 patients (75.0%) were able to sit without support for ≥ 30 seconds, and 2 patients each (16.7% each) were able to stand with assistance, stand alone, walk with assistance, and walk alone
- The improvements in Children's Hospital of Philadelphia Infant Test of Neuromuscular Disorders (CHOP INTEND) scores from baseline in both cohorts were sustained over time.
- Nearly all Cohort 2 patients (11/12, 91.7%) achieved a score ≥ 50 on the CHOP INTEND, approximating the range of scores for Type 2 SMA children reported in the Pediatric Neuromuscular Clinical Research Network (PNCR) study [23].
- Other clinically meaningful milestones were maintained 24 months after AVXS-101 infusion:
 - Of the 7 patients in Cohort 2 who did not require non-oral nutrition prior to AVXS-101 dosing, 5 (71.4%) maintained the ability to thrive
 - Eleven Cohort 2 patients (91.7%) were still able to swallow effectively enough to feed orally
 - Seven of 15 patients (46.7%) remained independent of ventilatory support

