8.2. Patient Exclusion Criteria

Patients must not meet any of the following exclusion criteria:

1. Previous, planned or expected scoliosis repair surgery/procedure prior to 18 months of age
2. Use of invasive ventilatory support (tracheotomy with positive pressure) or pulse oximetry < 95% saturation at screening
 - a. Pulse oximetry saturation must not decrease ≥ 4 percentage points between screening and dosing with confirmatory oximetry reading
 - b. Patients may be put on non-invasive ventilatory support for < 12 hours per day at the discretion of their physician or trial staff
3. Use or requirement of non-invasive ventilatory support for ≥ 12 hours daily in the 2 weeks prior to dosing
4. Patient with signs of aspiration based on a swallowing test or whose weight-for-age falls below the 3rd percentile based on WHO Child Growth Standards [42] and unwilling to use an alternative method to oral feeding
5. Active viral infection (includes human immunodeficiency virus [HIV] or positive serology for hepatitis B or C, or known Zika virus infection)
6. Serious non-respiratory tract illness requiring systemic treatment and/or hospitalization within 2 weeks prior to screening

7. Upper or lower respiratory infection requiring medical attention, medical intervention, or increase in supportive care of any manner within 4 weeks prior to screening
8. Severe non-pulmonary/respiratory tract infection (e.g., pyelonephritis, or meningitis) within 4 weeks before administration of gene replacement therapy or concomitant illness that, in the opinion of the Principal Investigator, creates unnecessary risks for gene replacement such as:
 - a. Major renal or hepatic impairment
 - b. Known seizure disorder
 - c. Diabetes mellitus
 - d. Idiopathic hypocalcuria
 - e. Symptomatic cardiomyopathy
9. Known allergy or hypersensitivity to prednisolone or other glucocorticosteroids or their excipients.
10. Concomitant use of any of the following: drugs for treatment of myopathy or neuropathy, agents used to treat diabetes mellitus, or ongoing immunosuppressive therapy, plasmapheresis, immunomodulators such as adalimumab, or immunosuppressive therapy within 3 months prior to gene replacement therapy (e.g., corticosteroids, cyclosporine, tacrolimus, methotrexate, cyclophosphamide, IV immunoglobulin, rituximab)

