5.3. Ability to Thrive ITT Population

The ability to thrive ITT population will consist of symptomatic patients with biallelic deletion mutations of *SMN1*, 2 copies of *SMN2* without the genetic modifier (c.859G>C), intact swallowing and receiving no enteral (mechanical) nutrition at baseline, who receive an IV infusion of AVXS-101 and have at least one post-baseline efficacy evaluation.

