5.6. PNCR Control Population

The PNCR Natural History dataset is drawn from a large natural history study ([Finkel, 2014](#)) performed on a large cohort of 337 patients with any form of spinal muscular atrophy followed at 3 large, internationally recognized tertiary medical centers with significant expertise in the management of SMA (Harvard University/Boston Children's Hospital, Columbia University and the University of Pennsylvania/Children's Hospital of Philadelphia). Previously identified patients followed in PNCR site clinics and newly diagnosed patients were enrolled. All eligible patients were offered participation in the PNCR study. Study visits were scheduled at baseline and at 2, 4, 6, 9, and 12 months and every 6 months thereafter. The SMA standard of care

guidelines ([Wang, 2007](#)) were used as a basis for providing uniform care among the study sites. For purposes of this study, sitting (for SMA Type 2) was defined as being able to sit independently for >10 seconds; children who were unable at any point to achieve this milestone were classified as SMA Type 1.

A natural history control population is drawn from the PNCr Natural History Dataset ([Finkel, 2014](#)) consisting of all patients with age of onset ≤ 6 months, bi-allelic deletion of *SMN1* (exon 7/8 common homozygous deletion) and 2 copies of *SMN2* for whom enrollment data (retrospective and prospective) is available to determine survival based on the defined criteria. The *SMN2* modifier mutation (c.859G>C) described by Prior and colleagues (Prior, Thomas W., et. al. "A positive modifier of spinal muscular atrophy in the *SMN2* gene." *The American Journal of Human Genetics* 85.3 (2009): 408-413.) was not assessed in the PNCr study cohort. Based on these criteria, 23 patients from the PNCr dataset are included in the control population. Among them, 16 patients reached the combined endpoint of death or the need for a minimum of 16 hours/day of noninvasive ventilation support for a minimum of 14 continuous days by 14 month of age and one patient discontinued the study at age of month 4. The survival rate at 14 months of age is approximately 25% (6/23), of which the control cohort will be used as comparator with ITT population for survival analysis.

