8.3.18. Proportion of patients maintaining the Ability to Thrive

The ability to thrive is defined by meeting all of the following criteria:

- the ability to tolerate thin liquids as demonstrated through a formal swallowing test
- does not receive nutrition through mechanical support (i.e., feeding tube)
- maintains weight ($>$ third percentile for age and gender as defined by WHO guidelines) at 18 months of age.

A patient who is not required mechanical support to receive nutrition at the date of 18 months of age visit is considered to meet the feeding criterion.

The observed proportion of patients maintaining the ability to thrive at 18 months will be compared to zero using a 1-sided Exact Binomial Test, along with the corresponding 97.5% confidence intervals. To make computation of the p-value possible, the value of 0.1% will be used in place of a literal zero.

Additionally, the proportion of patients meeting each of the criteria will be summarized in ability to thrive population.

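### Ventilator independence and ability to thrive are tested against a 0.1% null for which the documents give no untreated rate, so the two exploratory p-values cannot show benefit

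*SAP*

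**What the plan says.** For ventilator independence, SAP 8.3.17.4 states: "The observed proportion achieving independent of ventilator support at 18 months of age will be compared to zero using a 1-sided Exact Binomial Test". For ability to thrive, SAP 8.3.18 states: "The observed proportion of patients maintaining the ability to thrive at 18 months will be compared to zero using a 1-sided Exact Binomial Test". Both sections explain the working null in the same way: "To make computation of the p-value possible, the value of 0.1% will be used in place of a literal zero". SAP 6.1 sets the one-sided level at 0.025. Both sections also plan 97.5% confidence intervals.

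The 0.1% value comes from SAP 3.7 and Protocol 14.2, where it is the null for the primary endpoint. The argument there is that untreated patients are not expected to sit, roll over, stand or walk. Ventilation, swallowing, feeding and weight are not mentioned.

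Protocol 8.2 limits ventilator use at entry by excluding invasive support and "Use or requirement of non-invasive ventilatory support for ≥ 12 hours daily in the 2 weeks prior to dosing". Infants on no support, or on less than 12 hours a day, can enrol. SAP 5.3 defines the Ability to Thrive ITT population as having "intact swallowing and receiving no enteral (mechanical) nutrition at baseline".

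SAP 8.3 places the exploratory efficacy analyses on the Efficacy Completers Population. Protocol 14.1.1.2.2 assigns the ability-to-thrive proportion to the Ability to Thrive ITT population.

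**The concern.** A one-sided test against 0.1% is informative only if an untreated infant almost never has the outcome. The plan argues this for motor milestones that the disease prevents. The two outcomes here are worded as retention: remaining independent of a ventilator and maintaining the ability to thrive. An infant who enters breathing and feeding unaided can be a success by keeping that state to 18 months.

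Elsewhere the SAP guards against counting what was already present. Motor milestones seen at baseline are not counted (SAP 4.2), and patients already at a CHOP-INTEND threshold are left out of that threshold's analysis (SAP 8.3.17.1 to 8.3.17.3). Neither rule reaches these two outcomes.

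What is at stake is interpretation. A small p-value would appear in the same format as the one for sitting, and a reader could take it as evidence of benefit over untreated disease. It shows only that the rate exceeds 0.1%.

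**Working it through.** **Inputs.** Null p0 = 0.001 (SAP 8.3.17.4, 8.3.18). One-sided level 0.025 (SAP 6.1). Planned enrolment 30 (Protocol 7.2; up to 30 in SAP 3.7). ITT minimum 25 (SAP 3.7).

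**Reproducing the plan's own figure.** For the primary endpoint SAP 3.7 claims power above 95% with 25 patients and a true rate of 20% to 50%. One responder is enough: P(X≥1) = 1 − 0.999^25 = 0.0247 under the null. Power at 20% is 1 − 0.8^25 = 0.996. The claim holds, and the same calculation applies to the two exploratory tests.

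**Which n applies.** Efficacy Completers are drawn from all treated patients, including those who die, discontinue for an adverse event or meet discontinuation criteria (SAP 5.4), so n is about 30. For ability to thrive the smaller set may apply. In Protocol 5.4 the Phase 1 result is reported as "Of the 7 patients in Cohort 2 who did not require non-oral nutrition prior to AVXS-101 dosing", out of 12. Assuming the same share of 25 ITT patients, 7/12 × 25 = 14.6, or about 15.

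**Successes needed against 0.1%.**

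| Result | p-value | Significant at 0.025 |
|---|---|---|
| 1/15 | 1 − 0.999^15 = 0.0149 | yes |
| 1/25 | 1 − 0.999^25 = 0.0247 | yes |
| 1/30 | 1 − 0.999^30 = 0.0296 | no |
| 2/30 | 1 − 0.999^30 − 30 × 0.001 × 0.999^29 = 0.0004 | yes |

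One success suffices up to n=25, and two are needed from n=26 to n=242.

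**Chance that an ineffective treatment is declared significant.** The documents give no untreated rate q for either outcome, so 1%, 5% and 10% are assumptions that show the range. At n=30 the probability is 1 − (1−q)^30 − 30q(1−q)^29. At n=15 it is 1 − (1−q)^15.

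| Assumed q | n=30 (two needed) | n=15 (one needed) |
|---|---|---|
| 1% | 1 − 0.7397 − 0.2242 = 3.6% | 1 − 0.8601 = 14% |
| 5% | 1 − 0.2146 − 0.3389 = 45% | 1 − 0.4633 = 54% |
| 10% | 1 − 0.0424 − 0.1413 = 82% | 1 − 0.2059 = 79% |

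The 2.5% level is kept at n=30 only if q is at most about 0.82%. At n=15 the limit is 1 − 0.975^(1/15), about 0.17%.

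**Untreated figures that the documents do give.** SAP 5.6 reports 6/23 (26.1%) event-free at 14 months, and Protocol 5.4 cites a natural-history rate of 8%. Both concern survival free of permanent ventilation. Ventilator independence means no daily use at all at 18 months, which is stricter. In Phase 1 all 15 treated patients were alive without permanent ventilation, yet only 7 of 15 (46.7%) were ventilator-independent (Protocol 5.4). The two figures are therefore rough ceilings for ventilator independence, and no figure is given for thriving.

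**The case against.** The strongest reply is that little depends on these tests. They are exploratory and outside the hierarchy in SAP 8.4. The SAP says openly that 0.1% stands in for zero, and neither section claims superiority to natural history. Intervals are printed beside the p-values: read as two-sided exact 97.5% limits, 2/30 gives 0.6% to 24.5%, so the uncertainty is visible. SAP 4.7 also leaves room for natural-history comparisons. All of this stands and limits the point to reporting. It does not supply a basis for the null.

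It can also be said that retention is only part of the picture. Thriving requires weight above the third percentile at 18 months, which is not a baseline condition of the thrive population. Infants on less than 12 hours of support could gain independence. That is correct: success can largely reflect the state at entry, but need not.

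Two stronger readings are tempting. A reader might infer that 0.1% is false, or that a significant 2/30 (6.7%) falls short of the 8% natural-history rate. The documents support neither, because 8% and 6/23 measure a less demanding outcome and cannot serve as benchmarks. A reader might also infer that a single ventilator-independent infant would be significant. That is so only at n of 25 or fewer, whereas the set assigned to this test has about 30.

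**Conclusion.** The concern holds in a limited form. The 0.1% null is unsupported for ventilator independence and ability to thrive, and no baseline rule separates retained from gained successes. Rejecting it therefore does not show benefit over untreated disease.

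The size depends on an untreated rate that the documents do not give. At n=30 the nominal level survives if that rate is below about 0.82%, and error reaches 45% at an assumed 5%. On a thrive set of about 15, itself an assumption from the Phase 1 share, error is already 14% at an assumed 1%.

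Severity is minor. The effect is confined to exploratory reporting, and the primary and secondary conclusions are untouched.

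**What to change.** In SAP 8.3.17.4 and 8.3.18:

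- Delete the comparison to zero and the 0.1% substitution.
- Keep the counts, percentages and 97.5% confidence intervals, and state that they use the exact method named for the primary endpoint in SAP 8.1.1. That section already falls back on description alone for subgroups without a suitable comparator.
- In 8.3.17.4, show independence at 18 months by the baseline ventilator-use category already summarised under SAP 6.2.4.2, so that retained and gained independence can be told apart.
- In 8.3.18, name one denominator and reconcile SAP 8.3 (Efficacy Completers) with Protocol 14.1.1.2.2 (Ability to Thrive ITT population).

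The cost is SAP wording and one cross-tabulation of data already collected. Two exploratory p-values are lost. The primary test, the secondary test and the hierarchy stay as they are.

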8.3.18. Proportion of patients maintaining the Ability to Thrive

The ability to thrive is defined by meeting all of the following criteria:

- the ability to tolerate thin liquids as demonstrated through a formal swallowing test
- does not receive nutrition through mechanical support (i.e., feeding tube)
- maintains weight ($>$ third percentile for age and gender as defined by WHO guidelines) at 18 months of age.

A patient who is not required mechanical support to receive nutrition at the date of 18 months of age visit is considered to meet the feeding criterion.

The observed proportion of patients maintaining the ability to thrive at 18 months will be compared to zero using a 1-sided Exact Binomial Test, along with the corresponding 97.5% confidence intervals. To make computation of the p-value possible, the value of 0.1% will be used in place of a literal zero.

Additionally, the proportion of patients meeting each of the criteria will be summarized in ability to thrive population.

8.3.19. Age of Achievement of Independent Sitting (for 10 seconds)

The ability to sit independently will be defined as by WHO MGRS. Descriptive statistics will be presented for these endpoints, for patients that achieve functional independent sitting, including mean, standard deviation, median, minimum, and maximum values. Milestone of Independent Sitting collected outside of SAP-defined visit window of Month 18 of age visit will be included in the analysis.

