14. Proportion of patients that achieve the ability to walk alone as defined by WHO Motor Developmental Milestones ([Appendix 5](#)) [38].
15. Improvement of raw score from baseline to the maximum using BSIDv03, Fine and Gross Motor Function Subtests ([Appendix 3](#)).
16. Maximum change from baseline in CHOP INTEND score ([Appendix 6](#)).
 - a. Proportion of patients achieving CHOP INTEND score ≥ 40 ([Appendix 6](#)).
 - b. Proportion of patients achieving CHOP INTEND score ≥ 50 ([Appendix 6](#)).
 - c. Proportion of patients achieving CHOP INTEND score ≥ 58 ([Appendix 6](#)).
17. Proportion of patients with the ability to remain independent of ventilator support, defined as requiring no daily ventilator support/usage at 18 months of age.
18. Proportion of patients maintaining the ability to swallow and to maintain weight ($>$ third percentile based on WHO Child Growth Standards for age and gender [42]) without need of gastrostomy or other mechanical or non-oral nutritional support
19. Age at which patient first achieves WHO MGRS sitting without support (10 seconds) ([Appendix 5](#))

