3.5. Study Design

This is a Phase 3, open-label, single-arm, single-dose trial of AVXS-101 (gene replacement therapy) in patients with SMA Type 1 with one or two copies of *SMN2*. Up to 30 patients < 6 months (< 180 days) of age at the time of gene replacement therapy (Day 1) will be enrolled.

The trial includes 3 trial periods: screening, gene replacement therapy, and follow-up (**Error! Reference source not found.1**). During the screening period (Days –30 to –2), patients whose parent(s)/legal guardian(s) provide informed consent will undergo screening procedures to determine eligibility for trial enrollment. Patients who meet the entry criteria will enter the in-patient gene replacement therapy period (Day –1 to Day 3). On Day –1, patients will be admitted to the hospital for pre-treatment baseline procedures. On Day 1, patients will receive a one-time intravenous (IV) infusion of the equivalent of AVXS-101 cohort 2 dose received in the AVXS-101-CL-101 trial over approximately 30-60 minutes, dependent upon required total volume, and will undergo in-patient safety monitoring over the next 48 hours. Patients may be discharged 48 hours after gene replacement therapy, based on Investigator judgment. During the outpatient follow-up period (Days 4 to End of Trial at 18 months of age), patients will return at regularly scheduled intervals for efficacy and safety assessments until the patient reaches 18 months of age. Any missed visit should be rescheduled as soon as possible, but within the visit windows specified in the schedule of assessments.

All post-treatment visits will be relative to the date on which gene replacement therapy is administered, until the patient is 14 months of age, after which will be relative to the patient's date of birth. For the 14 and 18 months of age visits, the patient will return within 0 to 14 days after the date on which the patient reaches 14 and 18 months of age, respectively. The 18 months of age visit will also serve as the End of Trial visit. After the End of Trial visit, eligible patients will be asked to participate in the long-term follow-up trial.

Figure 1: Study Design Schematic

Note: After the End of Trial visit at 18 months of age or at the time of early discontinuation patients will be invited to participate in a long term follow up study conducted under a separate protocol.

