6.2.3. Definition of Final Treatment Value

The first non-missing value on or after the participant reaches 14 months of age will be considered for the purposes of the secondary endpoint survival without permanent ventilation. There is no upper bound for the “14 months” age visit; that is, no visit is too late to represent the “14 months of age” analysis. The earliest visit on or after 420 days of age will be used in the “14 months of age” analysis.

Due to the COVID-19 pandemic, patients with the end of study (EOS) visit planned between Feb, 2020 and Sept, 2020 may not be able to complete the EOS visit in the protocol defined visit window. Based on current guidance, these patients will be allowed to complete the EOS when hospitals reopen for normal operation.

For developmental milestones, CHOP-INTEND score and Bayley scale, the final treatment value for each patient is defined as the first non-missing value on or after the participant reaches 18 months of age (540 days) with an upper limit of 570 days. Thus, the earliest visit between 540 and 570 days of age, inclusive, will be used in the “18 months of age” analysis. For other non-safety measures, the definition of final treatment value will be footnoted in the corresponding tables, listings or figures.

For safety data collected through the EOS visit will be used for safety analysis, no upper bound for final treatment value.

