6.4.1. Study Day Based Visit Windows

For efficacy analysis, the time windows specified in [Table 4](#) describe how efficacy data will be assigned to protocol-specified time points, as displayed in the Schedule of Assessments in [SAP Section 3.5.1](#). All time points and corresponding time windows are defined based on Dosing Date.

If more than one efficacy observation for a specific assessment is included in a time window, the assessment closer to the nominal time will be used. If there are two efficacy observations equally distant to the nominal time, the latest one will be used in analyses. Any efficacy assessments occurring outside the analysis windows will be considered an assessment of an unscheduled visit.

Table 4: Study Day Based Visit Window

| Scheduled Visit | Nominal Days (Study Day) | Acceptable Analysis Window in Study Days (Min Day – Max Day) |
|--|--------------------------|--|
| Baseline | - | <1 |
| Month 1 | 30 | 1 to 44 |
| Month 2 | 60 | 45 to 74 |
| Month 3 | 90 | 75 to 104 |
| Month 4 | 120 | 105 to 134 |
| Month 5 | 150 | 135 to 164 |
| Month 6 | 180 | 165 to 194 |
| Month 7 | 210 | 195 to 224 |
| Month 8 | 240 | 225 to 254 |
| Month 9 | 270 | 255 to 284 |
| Month 10 | 300 | 285 to 314 |
| Month 11 | 330 | 315 to 344 |
| Month 12 | 360 | 345 to 374 |
| Month 13 | 390 | 375 to 404 |
| Month 14 | 420 | 405 to 434 |
| Month 15 | 450 | 435 to 464 |
| Month 16 | 480 | 465 to 494 |
| Month 17 | 510 | 495 to 539 |
| Month 18 | 540 | 540 to 569 |
| Month K | K*30 | K*30 to (K+1)*30-1 |
| Final Treatment Visit and 14 Months of Age Analysis Window | | 0 to ≤14 days after patient reaches 14 months of age (420-434 days of age) visit window; 0 to ≤14 days after patient reaches 18 months of age (540 days of age) visit window |

*Depending on age at time of dosing, patients will complete varying number of visits. The patient must complete a visit within 2 weeks after reaching 14 months of age; subsequent visits will be scheduled from that visit date. The patient must also complete the final study visit within 2 weeks after reaching 18 months of age.

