Due to COVID-19 pandemic, a few patients may complete the final visit (18 months of age) months outside of protocol-defined visit window. Summary tables for efficacy analysis will be created based on the visits up to month 18 of age and any data collected after month 18 of age visit to the end of study visit will be grouped into “Month 19 of age and older. Data collected through the final visit will be presented in the listings. In case, multiple record falls within “Month 19 of age and older” visit then first record will be used for analysis.

Safety data, such as laboratory results, vital signs, ECGs, and physical exams will be assessed by date and study day. For lab data collected on an unscheduled visit, the protocol defined visit windows will be applied. For change from baseline analyses the value associated with the scheduled visit will be used. Due to the visit window (± 7 days) for Day 60 visit and Day 72

visit, there is an overlap when assigning data to these two visits. Data collected between Day 53 to Day 66 will be assigned to Day 60 visit. Data collected between Day 67 to Day 79 will be assigned to Day 72 visit. For summaries of shifts from baseline and potentially significant values, all post baseline values will be considered for these analyses. Baseline for safety measures will be defined as the latest value before Day 1.

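### SAP 8.3.19 summarises age at first sitting in achievers only and pools sitters from delayed final visits, so it is not the typical age of treated infants and can mask part of a delay

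*SAP*

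**What the plan says.** Age at first sitting without support for 10 seconds is the last of the exploratory endpoints in Protocol 14.1.1.1.3. The lead-in to that list defines a responder as an infant who achieves the endpoint at a post-procedure visit no later than the 18-month visit.

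SAP 8.3.19 gives the whole analysis: "Descriptive statistics will be presented for these endpoints, for patients that achieve functional independent sitting". The statistics listed are the mean, SD, median, minimum and maximum. It then adds: "Milestone of Independent Sitting collected outside of SAP-defined visit window of Month 18 of age visit will be included in the analysis". No censoring rule, time-to-event method, test or comparator is named. Kaplan-Meier estimation appears only for survival (SAP 8.2.1). The date of achievement is the earliest video recording that central review confirms (SAP 6.2.4.3).

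On follow-up, SAP 3.5 states: "The 18 months of age visit will also serve as the End of Trial visit". SAP 6.4.1 adds: "The patient must also complete the final study visit within 2 weeks after reaching 18 months of age". For milestones, SAP 6.2.3 sets the analysis window: "the earliest visit between 540 and 570 days of age, inclusive, will be used in the “18 months of age” analysis". SAP 6.4.1 expects exceptions because of the pandemic: "a few patients may complete the final visit (18 months of age) months outside of protocol-defined visit window".

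The primary analysis (SAP 8.1.1) counts sitting up to and including the 18-month visit in the ITT population. It admits later sitting only in sensitivity analyses. SAP 8.3 bases the exploratory analyses on the Efficacy Completers population.

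**The concern.** Age at sitting is observed only if it falls before follow-up ends. A mean or median over those who sat describes the early part of the cohort and leaves out every infant who had not sat. If most infants sit, this matters little. If half or fewer do, the figure can be far from the age at which a treated infant typically sits, and it moves less than it should when sitting is later.

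Pooling post-window sitters raises a second problem. An infant seen on time has no chance of contributing an age beyond the window; an infant whose final visit slipped by months does. The summary therefore mixes unequal follow-up, and its sitters need not be those counted in the primary endpoint.

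At stake is how one exploratory table is read. No confirmatory conclusion depends on it.

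**Working it through.** **Inputs from the documents.** Planned response 20% to 50%, n = 25, null rate 0.1%, one-sided alpha 0.025 (SAP 3.7). Phase 1 Cohort 2 had 9 of 12 = 75% sitting for 30 seconds (Protocol 5.4), used here only as a higher scenario. An on-time final visit falls at 540 to 554 days, and 554/30 = 18.47 months on the SAP's 30-day month. The milestone window ends at 570 days.

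**Not in the documents, so assumed.** The shape and spread of sitting ages, and the number and length of delayed visits.

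**Step 1: the plan's own figure.** None is given for age at sitting. The nearest is the power of the primary test.
- P(at least 1 of 25 at 0.1%) = 1 − 0.999^25 = 0.0247, so one sitter is enough to reject.
- Power at 20% is 1 − 0.8^25 = 0.996; at 50% it exceeds 0.999.

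The stated power above 95% is reproduced. The planning range is thus one in which 50% to 80% of infants do not sit.

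**Step 2: who can be a late sitter.** The trial ends at the 18-month visit, due within 14 days. Family videos are accepted during the trial (Protocol 11.3). Sitting after day 570 can therefore be recorded only in an infant still in the trial then, that is, one with a delayed final visit. The SAP does not say this outright; it follows from these sections together.

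**Step 3: what the achievers' median estimates.** Take one cutoff and no loss before it. Rank infants by age at sitting, with non-sitters last. Achievers are the first share r, so their median sits at rank r/2. This needs no distribution and does not require that non-sitters would ever sit.

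| Response r | Achievers' median is cohort percentile | Cohort median by the cutoff |
|---|---|---|
| 20% | 10th | not reached |
| 50% | 25th | about at the cutoff |
| 75% | 37.5th | reached |
| 90% | 45th | reached |

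For example, 5 sitters among 25 infants make the reported median the third infant to sit.

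**Step 4: how much of a delay could be masked.** For a normal distribution cut at its r quantile, let a = z(r) and λ = φ(a)/r. The achievers' mean is low by λ SD, and the share of a small delay that does not show is λ(λ + a). At r = 50%: λ = 0.399/0.5 = 0.80 and the share is 0.80 × 0.80 = 64%. At 20%, 75% and 90% the mean is low by 1.40, 0.42 and 0.20 SD, and the share is 78%, 47% and 29%. It falls below half above about 71% response.

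A 2-month delay was also simulated with a cutoff at 554 days and no late visits. Share masked:

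| Assumed ages | r = 20% | 50% | 75% | 90% |
|---|---|---|---|---|
| Normal, SD 3 months | 82% | 70% | 55% | 39% |
| Normal, SD 4 months | 81% | 68% | 53% | 36% |
| Lognormal, sigma 0.3 | 71% | 57% | 42% | 27% |
| Exponential from 6 months | 46% | 39% | 30% | 19% |

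All four shapes assume that every infant would sit eventually. The same delay lowers the proportion sitting by the cutoff from 50% to between 25% and 44%.

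**Step 5: effect of pooling late sitters.** Assume 20% of final visits are 1 to 3 months late. At 50% response the achievers' mean rises by 0.16 to 0.31 months (normal, SD 4: 15.27 to 15.57), and the share counted as sitters rises from 50% to between 51.1% and 54.9%. Pooling moves the average up.

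**The case against.** The endpoint is exploratory, descriptive and outside the testing hierarchy (SAP 8.4), and the SAP says plainly that the summary covers achievers. Non-sitters are not lost to the trial: they count as failures in the primary proportion (SAP 6.3), where a delay would also show. All of this stands and limits the weight of the point.

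A reader might infer that the summary hides most of any delay. The documents do not support that. It holds at 20% to 50% response under normal or lognormal ages, but not under the exponential shape, and it is borderline or false at about 75% and above. The plan itself expects at least 50%.

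A reader might also attach a number of months to the understatement. That would need a distribution of ages and the assumption that every infant eventually sits. If the non-sitters never would, there may be no finite cohort median to understate, and the achievers' mean fairly describes age among responders.

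Nor do late sitters add to the understatement: they raise the mean. Their fault is unequal follow-up. Few are expected, and SAP 8.1.1 has a matching sensitivity analysis of the primary endpoint.

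Finally, the protocol's responder rule is worded by visit, so a much delayed final visit might still be called the 18-month visit. That is weak: the protocol gives that visit a 14-day window, and SAP 8.3.19 itself describes these data as outside its window.

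**Conclusion.** The point holds as a matter of what the statistic means. Whenever some infants do not sit, the achievers' median lies below the cohort median or stands in for one that is not reached. It is the 10th to 25th percentile at the planned response and the 37.5th at 75%. This rests only on a common cutoff and no loss before it. The statistic can mask part of a delay, in the assumed cases 19% to 82% of a 2-month shift; no single figure is justified, because the documents give no distribution of sitting ages.

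Pooling post-window sitters departs from the protocol's responder definition and from the primary analysis, and SAP section 13 does not list the departure. That only delayed visits can supply these ages is an inference, though a firm one. This is a cheap improvement to an exploratory table and does not threaten the primary result.

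**What to change.** In SAP 8.3.19, for the ITT population, report the cumulative incidence of first centrally confirmed sitting by age, at 12, 15 and 18 months, with the median if reached.

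- Make death the only competing event. Permanent ventilation should not be one, because the primary endpoint does not disqualify a ventilated infant who sits.
- Censor non-sitters at their last milestone assessment, with one age cutoff for all at 570 days. Treat the outcomes of in-window final visits as tied at that cutoff; otherwise a sitter seen late in the window is set against a risk set already emptied by censoring.
- Keep the achievers' mean, SD, median and range, labelled as among achievers, with n/N and the same cutoff.
- Show post-window sitters only in a sensitivity analysis or listing, in line with SAP 8.1.1.

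The cost is one table and one figure from dates already derived under SAP 6.2.4.3. The median may not be reached. With withdrawals censored, the 18-month estimate may differ slightly from the primary proportion, which counts them as non-achievers; a footnote should say so.
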